2. STUDY SUMMARY

Health care personnel (HCP) frequently receive annual influenza vaccinations and a substantive proportion of them might have attenuated or no response to additional standard dose influenza vaccines. In this population that is seasonally exposed to influenza illnesses and repeatedly vaccinated using standard dose (SD) vaccines, adjuvanted (AD) vaccines might elicit a better immunity than the typically used SD. We therefore propose to conduct a double-blinded randomized controlled vaccine trial among HCPs to determine if AD influenza vaccines generate superior seroprotection against influenza than SD vaccines particularly among previous sub-optimal responders.

The trial will be conducted at two hospital sites in Lima-Peru during the 2022 influenza season. It has annual circulation int the country, but with increases during the months of June to October, which coincides with winter. The study is aimed to HCP who were enrolled in the Cohort study of Influenza and other Respiratory Viruses among HCP in Peru (approximately 1500). The number of participants to be enrolled is 800 approximately. The study design is a randomized, double-blind vaccine trial. Eligible HCP at each site who consent to participate will be randomized 1:1 to receive either a single dose of AD (FLUAD, quadrivalent, Seqirus) or SD (VaxigripTetra, quadrivalent, Sanofi-Pasteur). Participants, researchers and laboratory staff performing the assays will be blinded to the vaccine information.

Participants will be invited to attend the study site for a study screening and assessment of eligibility criteria, if they agree to participate and once consent form is signed, they will visit the site at day 0 for vaccination and medical assessment. Another brief medical adverse event assessment will be performed on days 3 and 7. Participants will be also prompted to begin active surveillance for acute illnesses as soon as US Center of Prevention and Control of Disease (US CDC) and the study site PI confirm that seasonal influenza is circulating locally or there are indicators that circulation is imminent. During the influenza season, participants will be followed up twice a week via SMS or phone calls to assess if they become sick with a respiratory event, if so, they will be asked questions about their illness through an acute illness survey and a swab sample will be requested.

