10.2 Sample size

We calculate that we will need a minimum sample size of 118 participants per vaccination group for detecting a difference between two proportions (based on seroprotection percentages for influenza A(H1N1p) of a previous study:91% vs 78% [21]) (see below), considering a 95% confidence level (two-sided) and 80% statistical power. To account for loss to follow up, we will increase sample size by 20%, so sample size will be a minimum of 142 subjects per group (Table 1).

Table 1. Sample size calculation based on published seroprotection rates for different influenza viruses

Seroprotection	P1 (AD group)	P2 (SD group)	n/per group	With additional 20%
subtypes				
Influenza A(H1N1p)	91%	78%	118	142
Influenza A(H3N2)	No information	No information		

Influenza B	No information	No information		
Where P1=percentage o	f seroprotection for AD g	roup and P2=percentage	e of seroprotection for S	D group

However, although the sample size calculation yields 142 participants per group, there may be different scenarios in which the difference between groups is shortened. In the following table, differences of 10-20% are estimated (Table 2). As a result of this calculation, it is estimated that a sample size of approximately 400 individuals per group will allow us to detect a difference of at least 10% considering a 78% seroprotection rate in the group vaccinated with non-adjuvant vaccine.

Table 2. Different scenarios in seroprotection rates (28 days post-vaccination) per group and sample size calculation

Seroprotection rate in SD group	Relative increase (5) in AD group vs SD group	n per group	Total n	With additional 20%
78%	10%	359	718	862
78%	20%	70	140	168
88g%	10%	131	262	314
88%	15%	58	116	140

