Laboratory- confirmed influenza illness rates in HCP receiving AD	Clinical	Comparison of persons who did and did not become sick with influenza after receiving the AD or SD	Person became sick with influenza after receiving AD or SD vaccine Person did not become	Nasal swab specimen tests positive for influenza by PCR	Quantitative Discrete	PCR assay (laboratory)
vaccine		vaccine	sick with influenza after receiving AD or SD vaccine	Nasal swab specimen tests negative for influenza by PCR		

Secondary Objective 6: To assess the adverse events among HCP receiving SD and AD influenza vaccines

				Criterios de	Tipo de	Instrumento de
Variable	Dimensión	Indicador	Valores	medición	variable/indicador	medición
	(Dimension)	(Indicator)	(Values)	(Measurement criteria)	(Type of variable/indicator)	(Measurement instrument)
Adverse events in HCP receiving AD vs. SD vaccine	Anticipated (Clinical)	Local reactions: pain on vaccination site, swelling, lump itching, bruising	Yes	Person had a local and/or systemic reaction(s) after receiving AD or SD vaccine	Quantitative Discrete	Post-vaccination surveillance via follow-up visits and monitoring (calls, surveys)

	AND/OR Systemic reactions: fever (≥38°C), muscle ache, joint pain, headache, malaise, fatigue, weakness, sweating, shivering	No	Person did not have a local and/or systemic reaction(s) after receiving AD or SD vaccine		
	Death, life- threatening adverse event, hospitalization or prolongation of existing	Yes	Person had a serious adverse event after receiving the AD or SD vaccine		Post-vaccination surveillance via
Serious, Unanticipated (Clinical)	hospitalization, a persistent or significant incapacity affecting normal life activities, and other unanticipated event that seriously impacts the health of participants	No	Person did not have a serious adverse event after receiving the AD or SD vaccine	Quantitative Discrete	follow-up visits, monitoring (calls, surveys), and hospitalizations

Below we describe the statistical tests that we will perform to address each primary and secondary objective, highlighting which study population will be included for each analysis. All statistical tests will be performed with a significance level of 5% and a statistical power of 80%.

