3) To examine whether the number of prior influenza vaccination during the preceding 10 years, as documented by medical records, modifies immune responses after receipt of vaccination with AD or SD influenza vaccine, at approximately 28 days after vaccination and at the end of season. The result variables will be the same as those of the matrix of variables in the main objective, examining the differences by the number of influenza vaccines received by health personnel (HCP) during the previous 10 years. We will evaluate the possible effects of repeat vaccination on the immunogenicity of AD and SD using multivariate logistic regression models. Other variables to consider in the model include age, sex, presence of chronic diseases, body mass index, smoking, and alcohol consumption due to possible confounding factors with the immune system's response to vaccination against HIV. influenza. All health personnel participating in the clinical trial will be included as a study population for these analyzes.

4) To analyze and identify risk factors for sub-optimal response (lack of seroconversion/seroprotection) to SD and/or AD influenza vaccines. The outcome variables will be the same as those of the matrix of variables in the main objective, examining the differences by the following variables: age (subdivided between age groups: 18-49 years, 50-65 years,> 65 years); sex (man, woman); presence of chronic conditions (diabetes, autoimmune disorder, asthma, blood disorder, chronic lung disease, cardiovascular disease, high blood pressure, HIV / AIDS, kidney disorder, liver disorder, metabolic disorder, neurological disorder); body mass index; smoking and alcohol consumption; previous laboratory confirmed influenza diagnosis; previous influenza vaccine. We will use generalized linear models (GLM) with Poisson or binomial link functions as appropriate to assess risk factors. Other variables to consider in the model include age, sex, presence of chronic diseases, body mass index, smoking, and alcohol consumption due to possible confounding factors with the immune system response to vaccination against HIV. influenza. All health personnel participating in the clinical trial will be included as a study population for these analyzes.

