To compare the post-vaccine immune response, in approximately 28 days after vaccination and at the end of the influenza season, among the HCP who did not have a history of influenza infection confirmed by PCR result during any of the 6 years during the previous cohort study (2016 to 2021); among those with information available during the 6- year cohort.	Post-vaccination immune responses, at approximately 28 days after vaccination and at the end of the season, among HCPs with no history of PCR- confirmed influenza infection.	Wilcoxon signed rank test.	ITTm2
Examine whether the number of prior vaccinations against influenza during the previous 10 years, as documented in the medical records, modifies the immune response after receiving the AD or SD vaccine in approximately 28 days after vaccination and at the end of flu season.	Immune responses after receiving the AD or SD influenza vaccine, approximately 28 days after vaccination and at the end of the season	Descriptive statistics: multivariable logistic regression model	ITTm
Analyze and identify risk factors for a suboptimal response (lack of seroconversion / sero protection) to standard dose (SD) and / or adjuvanted (AD) influenza vaccines	Risk factors for suboptimal response (lack of seroconversion / seroprotection)	Descriptive statistics. Generalized linear models (GLM) with Poisson or binomial functions as appropriate	ITTm

To assess rates of laboratory-confirmed influenza illness in the group that received the AD adjuvanted influenza vaccine compared to the group that received the standard dose SD influenza vaccine.	Laboratory confirmed influenza illness rates among HCP receiving influenza vaccines AD vs. SD	Descriptive statistics., Calculation of incidence densities. Multivariate Cox Regression Model.	ITTm
Security Analysis			
To assess adverse events among HCP who received SD and	Frequency of AE	Descriptive statistics and	Security
AD influenza vaccines		Z test to evaluate	Population
		differences in	
		proportions	

- Population by Protocol: All HCPs vaccinated with any of the research products.
- ITTm population: HCPs who, having been vaccinated, became ill and did not become ill with influenza after receiving the AD or SD vaccine.
- ITTm1 population: HCPs may, having been vaccinated, became ill with influenza after receiving the AD or SD vaccine at approximately 28 days after vaccination and at the end of the season.

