11.2.2 Serology analysis

Samples will be processed and then frozen at -20°C. Specimens will be stored at the local CDC-approved local laboratory for serologic testing and then will be shipped to the US CDC laboratory for serologic testing at the end of the study. Hemagglutination inhibition (HI) assay will be run in duplicate using a CDC-approved protocol. Standard procedures typically include preparing a turkey (for A/H1N1 and influenza Bs) or guinea pig red blood cells (RBC) (for A/H3N2) suspension and treating serum samples with receptor-destroying enzyme to remove nonspecific inhibitors. Nonspecific agglutinins are removed by serum adsorption with packed RBCs. Serum is diluted 2-fold starting from 1:10. The HI titer is the reciprocal of the serum dilution in the last well with complete hemagglutination inhibition.

The panel of influenza viruses to be included in the HI assay will be determined depending on locally circulating viruses during enrollment and historically, including viruses in circulation during the previous 2-6 years.

Samples will be also shipped to US CDC labs for additional testing with additional immunological assays for influenza and other respiratory pathogens (e.g. RSV, parainfluenza viruses, human metapneumovirus, adenoviruses, and coronaviruses) or other agents that cause respiratory diseases such as bacteria, as well as for the biorepository.

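### Objective 3 models the effect of prior vaccination only on yes/no serological outcomes; a log2-titre model adjusted for Day-0 titre should be added, because the logistic analysis is valid but inefficient

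*Combined protocol and SAP*

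**What the plan says.** In section 11.1, objective 3 takes its outcomes from the primary objective's variable matrix. That matrix gives seroconversion and seroprotection yes/no values, with the cut-offs set in section 10.13. The model is stated once in the text, "We will evaluate the possible effects of repeat vaccination on the immunogenicity of AD and SD using multivariate logistic regression models", and once in the summary table of analyses, "Descriptive statistics: multivariable logistic regression model". The listed adjustment variables are age, sex, chronic disease, body mass index, smoking and alcohol. Pre-vaccination titre is not among them, and no arm-by-prior-vaccination term is named.

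The assay yields more than a yes/no result. Section 11.2.2 says "Serum is diluted 2-fold starting from 1:10", and sections 2 and 10.7 schedule blood at Day 0, Day 28 and end of season. For the primary objective and objectives 1 and 2, section 11.1 compares HI GMT as well as proportions. For objective 3 it names no titre-scale model. The matrix labels the yes/no outcomes as continuous, which is inconsistent, but a logistic model cannot take a continuous titre in any case.

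**The concern.** Sections 2 and 8 justify the trial by the possibility that repeatedly vaccinated staff respond less well. Attenuation is a matter of degree, and objective 3 is where it is examined. A threshold outcome registers it only when a person crosses the threshold. From a Day-0 titre of 1:10, Day-28 titres of 1:320 and 1:80 are 32-fold and 8-fold rises, and both count as seroconverted and seroprotected. Where most people are already positive, as at the plan's own planning rates of 78% and 91% seroprotection, the binary outcome has little room to move. The analysis could then miss a modest effect of repeated vaccination, or miss that the adjuvanted vaccine offsets it, although the assay data could have shown it.

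**Working it through.** **Inputs from the documents.** Section 10.2 plans with "considering a 95% confidence level (two-sided) and 80% statistical power" and seroprotection of 91% (AD) and 78% (SD), and adds 20% for loss to follow-up. Section 10.4 caps enrolment at 800.

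**Inputs assumed.** Log2 titre is normal, half the participants have many prior vaccinations, and the shift is 0.25 SD. The 50% positive rate is an illustration.

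**1. The plan's own figure.** The unpooled two-proportion formula gives n = (1.960 + 0.842)² × (0.91×0.09 + 0.78×0.22) / 0.13² = 7.85 × 0.2535 / 0.0169 = 118 per group, and 118 × 1.2 = 142. Both match section 10.2. They concern the comparison between vaccines; nothing equivalent is given for objective 3.

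**2. Titre scale.** 800 / 1.2 = 667 evaluable, so 333 in each half. z = 0.25 / √(2/333) = 3.23 and power = Φ(3.23 − 1.96) = 0.897.

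**3. A cut of the same titre.** A positive rate p falls to p′ = Φ(Φ⁻¹(p) − 0.25). z = (p − p′) / √{[p(1−p) + p′(1−p′)]/333}.

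| p | p′ | z | Power | Loss against 0.897 |
|---|---|---|---|---|
| 50% | 40.1% | 2.57 | 0.730 | 17 points |
| 78% | 69.9% | 2.38 | 0.665 | 23 points |
| 91% | 86.2% | 1.94 | 0.493 | 40 points |

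**4. Sensitivity to the starting point.** The large-sample relative efficiency of the cut is φ(c)² / [p(1−p)], with c = Φ⁻¹(p): 0.64 at 50%, 0.51 at 78% and 0.32 at 91%. Starting from 80% power on the titre scale, this implies 61%, 52% and 36% on the binary scale. For a shift of 0.4 SD the loss is only about 2 points at 50% positive and 11 at 91%.

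**5. Modification by vaccine.** Suppose a 0.5 SD drop occurs in the SD arm only, with 166 per cell. On the titre scale z = 0.5 / √(4/166) = 3.22 and power is 0.896. On the logit scale power is 0.445 with starting rates of 78% (SD) and 91% (AD), and 0.63 with 78% in both arms.

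**6. Seroconversion as the protocol defines it.** Steps 3 to 5 cut a single titre, whereas section 10.13 cuts the rise from Day 0 unless the Day-0 titre is below 1:10. Simulation with that definition and 2-fold dilutions used 333 against 333, an assumed log2 SD of 1.5 for baseline and for rise, and a rise 0.4 log2 lower in repeat vaccinees:

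| Analysis | Power |
|---|---|
| log2 Day-28 titre adjusted for log2 Day-0 titre | about 85–91% |
| Seroconversion | about 43–75% |
| Seroprotection | about 2–47% |
| log2 Day-28 titre without Day-0 titre, equal baselines | 66–67% (seroconversion 69–75%) |
| log2 Day-28 titre without Day-0 titre, higher baselines in repeat vaccinees | 2–15% (seroconversion 43–71%) |

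The low ends for seroconversion and seroprotection arise when repeat vaccinees start with higher titres.

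**The case against.** The strongest reply is that the outcome scale is a design choice. The protocol defines sub-optimal response as lack of seroconversion or seroprotection, and logistic regression on declared outcomes is sound. The summary table also lists descriptive statistics, so titres by number of prior doses may still be shown. This stands as far as validity goes: a reader who infers that the planned model is wrong would go beyond the documents. It does not answer the inefficiency, because descriptive statistics commit to no adjusted titre comparison. The responder definition is the subject of objective 4, whereas objective 3 asks about immune responses more generally.

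Second, a reader might take the 17 to 40 points in the working as a fixed cost. The documents do not support that. They give no titre SD, slope, seroconversion rate or distribution of prior doses, and the loss changes with effect size and positive rate.

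Third, it is tempting to say that the cut-offs discard most of the titre information. The relative efficiencies show a loss of 36% at 50% positive, about half at 78%, and clearly more than half only near 91%, which is the AD planning rate for one strain.

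Fourth, seroconversion is a cut of the rise and already uses the Day-0 titre. From a baseline of 1:40, Day-28 titres of 1:320 and 1:80 are 8-fold and 2-fold rises, and seroconversion does tell them apart. This objection stands. It rules out replacing the planned models with a regression of Day-28 titre on the listed covariates alone, which can perform worse than the plan.

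**Conclusion.** The concern holds in a limited form. For objective 3 the plan names only a logistic model of yes/no outcomes although full titres are available, and for modest attenuation this is clearly less powerful than a baseline-adjusted titre model. The size depends on assumptions that the documents cannot settle. It is about 17, 23 and 40 points at 50%, 78% and 91% positive if the titre model has about 90% power, and less for large effects. With the protocol's own seroconversion rule and the assumed SDs, the contrast is about 85–91% against about 43–75%. The planned analysis is valid and the objective is secondary, so the change is recommended for efficiency and is not a correction of an error.

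**What to change.** In section 11.1, objective 3, add a pre-specified linear (or left-censored, for titres below 1:10) regression of log2 HI titre at Day 28 for each vaccine strain, and the same at end of season. Include log2 Day-0 titre, the covariates already listed, vaccine arm, number of prior vaccinations and the arm-by-number interaction. Report geometric mean ratios with 95% confidence intervals. Do not fit the Day-28 titre without the Day-0 titre.

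Keep the logistic models for seroconversion and seroprotection alongside, and align the objective 3 row of the summary table.

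No new visits, samples or assays are needed. The cost is SAP wording, one extra model per strain and time point, and results reported on two scales.

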8. JUSTIFICATION

An adjuvanted quadrivalent inactivated influenza vaccine (aQIV), FLUAD[®] Quad (Seqirus) has been licensed in 38 countries including the USA since 2015 for use in persons aged 65 years and older [1, 2].

FLUAD[®] Quad is a standard-dose influenza vaccine that contains an adjuvant named MF59. This adjuvant is naturally found in humans and enhances immune response to vaccination [1, 3].

Studies have shown a significantly improved immunogenicity and seroprotection among adults aged \geq 65 years who received an AD influenza vaccine when compared to those vaccinated with a non-adjuvanted SD [4, 5]. A randomized study by Cowling et al (2019) [4] showed that MF-59 vaccine, among other enhanced vaccines, presented significantly higher proportion of participants who achieved a 4-fold or greater rise in postvaccination titers from day 0 to Day 30, with a postvaccination titer \geq 40, a significantly higher geometric mean titer at Day 30, compared to those who received a standard dose vaccine. In addition, they observed a trend rise of vaccine-specific T-cells at 7 and 30 days postvaccination with MF59. Studies have also shown effectiveness of adjuvanted influenza vaccine against influenza-associated outcomes [6].

Studies not noted safety concerns, and while AD vaccine has been associated with increased reactogenicity compared with non-adjuvanted SD vaccine in some studies, these symptoms have generally been reported to be mild or moderate and self-limited [1, 3, 4, 7, 8].

Not all people who receive SD influenza vaccines develop a protective antibody response to influenza virus infections. Vaccinee characteristics can be associated with poor immunogenic response to influenza vaccination [9-17].

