10.1 Study population

Eligible adult participants (age 18 or older) will work in one of the selected healthcare facilities (Cayetano Heredia National Hospital, and Arzobispo Loayza National Hospital) and will meet the following inclusion criteria:

Inclusion criteria:

- Be aged ≥18 years old;
- Have participated in the healthcare personnel cohort study between 2016 and 2021.
- Work at the facility full-time (≥30 hours per week);
- Have routine, direct, hands-on or face-to-face contact with patients (within 1 meter) as part of a typical work shift, including, but not limited to, physicians, nurses, respiratory therapists, physical therapists, unit clerks, radiograph technicians, medical assistants, and transporters;

- Work at the facility for ≥1 year prior to enrollment and planning to continue working at the facility for one year after enrollment;

- Willing to receive influenza vaccination (either AD/SD)

-Women of childebaring age have to complete the following criteria:

- Negative urine pregnancy test performed by the study staff within 24 hours preceding receipt of vaccination
- Willing to use use another reliable form of contraception approved by the Investigator that they select to use for at least 2 months after receiving the vaccine. If they are not using, we will provide access to contraceptives.
- Do not be in breastfeeding period

Exclusion criteria:

- Be vaccinated against influenza in the current season (influenza season 2022)
- Have severe, life-threatening allergies against influenza vaccines, eggs or influenza vaccine components
- Have a history of Guillain-Barré Syndrome or other autoimmune diseases
- Received blood or blood products within 3 months before enrollment
- Be pregnant, confirmed by rapid pregnancy test

The participation from each subject will be from the enrollment (March approximately) until the end of the influenza season

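### Secondary objective 4 studies age in three bands although exact age is collected; the top cut misses the 65-and-older range by one year, and banding costs precision for an age trend

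*Combined protocol and SAP*

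**What the plan says.** Section 11.1, secondary objective 4, lists the risk factors to be examined for lack of seroconversion or seroprotection. Age comes first and is given in bands: "age (subdivided between age groups: 18-49 years, 50-65 years,> 65 years". The model follows: "We will use generalized linear models (GLM) with Poisson or binomial link functions as appropriate to assess risk factors". The next sentence names age a second time, now without bands: "Other variables to consider in the model include age, sex, presence of chronic diseases, body mass index, smoking, and alcohol consumption". It does not say whether that term is grouped or continuous, and no reason is given for the cut points.

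Section 8 says that the adjuvanted vaccine has been licensed "for use in persons aged 65 years and older". The immunogenicity evidence that it goes on to cite is also in people aged 65 or more.

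Section 10.1 sets a minimum age and no maximum ("Be aged ≥18 years old") and limits entry to working staff ("Work at the facility full-time (≥30 hours per week"). Section 10.4 records age at screening. Neither section gives an age distribution or an expected number per band.

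**The concern.** There are two separate points, of unequal weight.

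The first is alignment. The middle band mixes 65-year-olds, who fall within the age range quoted in section 8, with people aged 50 to 64, who do not. The top band leaves out the first year of that range. A reader who wants to compare the objective 4 tables with the evidence in section 8 would be comparing slightly different groups.

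The second is precision. Objective 4 is where the trial would show whether response changes with age among working adults, most of them younger than the licensed range. Three bands treat a 20-year-old and a 49-year-old as the same. In a full-time workforce the top band is likely to be small, so most of the age contrast rests on the single cut at 50. Exact age is already in hand, so this loss is avoidable.

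**Working it through.** The plan gives no figure for age to reproduce: its sample-size calculation concerns seroprotection by arm and does not involve age.

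**Boundary.** Objective 4 has 50-65 and over 65; section 8 has 65 and older. The two differ only at age 65. Under the distributions tried below, the share aged exactly 65 runs from about 0% to 3%. With the planned maximum of 800 participants (section 10.4), that is 0 to 0.03 × 800 = 24 people.

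**Information lost by banding.** For a linear age effect,

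loss = 1 − (between-band variance of age ÷ total variance of age).

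If ages are spread evenly and band k covers a fraction f_k of the range, the variance within that band is f_k² times the total and the band has weight f_k. The loss is therefore Σ f_k³.

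*Even from 25 to 70 (assumed), the plan's bands.* Widths are 25, 16 and 4 years of 45, because the middle band runs to the end of age 65.

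(25/45)³ + (16/45)³ + (4/45)³ = 0.171 + 0.045 + 0.001 = 0.217, or about 22%.

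*Even from 25 to 65 (assumed).* The top band is empty, leaving widths of 25 and 15 years of 40.

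(25/40)³ + (15/40)³ = 0.244 + 0.053 = 0.297, or about 30%.

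*Other assumed distributions, the plan's bands, minimum age 18:*

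| Assumed ages | Loss |
|---|---|
| Truncated normal, mean 35-50, SD 8-12, oldest 65 | 34% to 81% |
| Same, oldest 70 | 28% to 81% |
| Same, oldest 75 | 25% to 81% |
| Truncated normal, mean 55, oldest 75 | 20% to 27% |
| Even 18-65 / 18-70 / 18-75 | 33% / 25% / 19% |
| Even 18-80 | 16% |
| Two narrow peaks, at 32 and 57 | about 15% to 17% |

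The set runs from about 15% to 81%. Neither end is a hard limit.

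**Effect of moving only the upper cut to 65 or older.** For ages even from 25 to 70:

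(25/45)³ + (15/45)³ + (5/45)³ = 0.171 + 0.037 + 0.001 = 0.210.

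That is less than one percentage point better than 0.217. In the truncated normal cases with mean 35-50 the gain is at most about 1.5 points, and at mean 55 up to about 4. Moving the cut brings alignment and almost no precision.

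**What the loss means for a test.** Suppose a linear age term had 80% power at two-sided 5%, so that its non-centrality is (1.96 + 0.84)² ≈ 7.85. The three-band test has two degrees of freedom and non-centrality 7.85 × (1 − loss). Its power would be about 58% at a 25% loss and 41% at a 50% loss.

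**The case against.** The strongest reply is that the plan may already do what is asked. Age appears a second time as a model covariate with no bands, and the summary table at the end of section 11.1 lists descriptive statistics beside the generalized linear model for this objective. The bands could be for tables, with a continuous term in the model. This stands in part: it cannot be said that every use of age in objective 4 is grouped. But the bands are attached to age as a risk factor and the form of the covariate is left open, so the wording still needs settling.

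A second reply is that 65 and older is not a category that objective 4 must follow. No objective concerns a licensed-age subgroup, section 12 says that the adjuvanted vaccine is not authorised in Peru, and few full-time staff will be exactly 65. This stands, and it keeps the boundary point small. A band of 65 or older would itself be small.

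Two stronger readings are tempting. A reader might infer that banding throws away at least a quarter of the information on age. A single cut at 50 does lose 1 − 3(25/45)(20/45) = 26% for ages even from 25 to 70, but the plan has three bands and loses about 22% there. With no age distribution in the documents, no minimum loss can be claimed. A reader might also infer that the response of people aged 65 and older could not be recovered from the trial. It could, because age is recorded at screening and a separate table can be made.

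**Conclusion.** The point holds as a minor one about a secondary analysis. The top cut does not match the age range in section 8, and this affects only participants aged exactly 65, probably few. Banding age as a risk factor loses precision for a trend: about 22% or 30% in the two evenly spread cases, and about 15% to 81% over the distributions tried. These figures rest on assumed age distributions and on a linear effect. If response changed in a step near one of the cuts, bands would lose less. The form of age as a covariate in the objective 4 model is unstated. The documents do not support calling the bands an error that hides the response of older staff. The randomised comparison for the primary objective is untouched.

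**What to change.** In section 11.1, secondary objective 4, state that age enters the generalized linear model as a continuous term, linear or as a restricted cubic spline, and that this is the main analysis of age. Say that the same term serves where age is an adjusting covariate. Use 18-49, 50-64 and 65 or older for descriptive tables only.

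The cost is a change of wording, a little more analysis work, and an age effect that is slightly less simple to present than three rows of a table. No new data are needed.
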